### **7.4.3 Intermediate Research Visits**

#### **7.4.3.1 Research Visits (In person, Days 1-3, 30-60 minutes)**

- Participants will complete assessments of withdrawal, craving, and substance use in-person daily for 3 days. The visits will occur either at the ED or at other clinical research space on Bellevue/NYU campus. In light of the health safety risks associated with the COVID-19 pandemic, interviews may be conducted remotely, rather than in-person, using an approved, secure audio or audio-video connection (e.g., telephone, Cisco Webex) from a setting offering adequate privacy. Participants will be advised that they may disconnect their video feed.
- Participants will assess themselves for symptoms of opioid withdrawal using subjective scales
- At the first visit (Day 1-3) in which the participant has objective signs of withdrawal, the participant will be provided with a prescription for BUP. If the participant does not have objective signs of withdrawal by the Day 3 visit, the prescription will be written at the conclusion of that visit. The prescription will be electronically sent to the participant's pharmacy for BUP or BUP/Nx 8/2mg: 2 films/tabs taken SL daily for each day, starting immediately, with a quantity sufficient to last until the scheduled appointment for

Study Number: s19-01700

Version: 7.0

Version Date: 08/01/2022

ongoing treatment)

- Participants will be assessed for adverse events, which will be recorded and reported.

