### **6.9.4 Dosing and Administration**

All participants will receive a total dose of BUP 32mg sublingually in divided doses during the index ED visit. After the participant has received a total of 8mg (as a single dose or in divided doses), BUP SL 24mg will be administered (i.e., 8mg + 24mg, or 4mg + 4mg +24mg). A dose of up to BUP 8mg SL may be administered by the clinical provider prior to enrollment of the patient-participant (i.e., given clinically, not as a research procedure).

After pre-medication assessments are complete and the participant is confirmed to have a COWS of  $\geq 8$ , the participant will be given BUP SL to reach a dose of 8mg. Starting 30 minutes after BUP administration, the participant will be reassessed for withdrawal severity and any adverse events. As long as there are no unexpected significant adverse events, an additional BUP 24mg SL will be administered. Then, participants will be monitored and reassessed every 30 minutes for a period of at least 90 minutes after receiving the last dose of BUP.

Participants will return on days 1, 2, and 3 for research visits. At those visits, participants will be assessed for opioid withdrawal using the COWS scale. On the first day that the participant has objective signs of opioid withdrawal (via COWS), the [name], who is a licensed physician with an X-waiver for BUP prescription, or another study clinician (with the appropriate license and X-waiver) will electronically send a prescription the participant's preferred outpatient pharmacy for a daily dose of BUP 16mg (BUP or BUP/NX 8/2mg: two SL) to start immediately. Participants will be prescribed a quantity sufficient to ensure medication coverage until the date of their appointment for ongoing treatment with a (non-study) OUD treatment provider. Participants who do not exhibit opioid withdrawal at any of the visits on days 1-3, will be given a prescription upon completion of the day 3 visit with instructions to self-administer upon emergence of symptoms of opioid withdrawal or craving.

All participants will receive a referral to be seen by a provider experienced in treating OUD. Thereafter, continued treatment and specific daily dosage of BUP-NX will be a joint decision between the study participant and the healthcare provider.

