### **6.9.9 Tracking of Dose**

On days 1 – 3, following the index visit, participants will participate in in-person research visits and complete various assessments which will include objective and subjective measures of withdrawal and craving, and side effects. Participants will follow-up by phone at one month and again be asked to report adherence, as well as other substance use (Details of assessments can be found in Sections 7.1 and 7.3).

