#### **7.4.4 Final Study Visit (Phone)**

##### ***Final Study Phone Check In (Day 30+-3, 30 minutes)***

- A healthcare utilization review and health questionnaire will be conducted to collect information on the type and amount of services received by participants.
- Functional outcome will be assessed using tools selected from the Study Measures.
- Attendance at follow-up treatment appointment within 1 month will be assessed by participant self-report and verified by contact with the provider.
- Participants will be assessed for adverse events, which will be recorded and reported.

At the conclusion of the study, the specifics of continued treatment will be a joint decision between the participant and the provider and will be managed by providers on a case-by-case basis. These decisions will not be reported to the study team. The novel part about this study is the induction strategy, but patients will otherwise be maintained on BUP in accordance with the standard of care. If patients wish to continue treatment, they will be connected with follow-up. The decision to continue will be a joint decision between the patient and provider.

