##### ***Unscheduled Visit***

If a patient is experiencing objective signs of withdrawal outside the hours of one of their research visit appointments, they may present to the Emergency Department for treatment. They will be asked to report this visit to the study team. The PI may be contacted 24 hours a day, seven days a week.

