## 10 Statistical Considerations

### 10.1 Statistical and Analytical Plans (SAP)

The overall findings of the study will be used to assess the feasibility, acceptability, and utility of initiating a BUP loading dose in ED patients and linking patients to ongoing OUD treatment. Statistical analyses will consist of descriptive analyses for the primary outcome (proportion of participants successfully induced via loading dose), and secondary outcome measures (opioid withdrawal and craving scores, time to next BUP dose, opioid and other illicit drug use, proportion making a successful transition to an outpatient clinic). Measures of central tendency (the mean), and the variability (standard deviation) of the study participant characteristics and for other participant-reported or objectively evaluated measures will also be calculated. Summary tabulations and measures of central tendency, variance, and other distributional properties of the obtained results will be presented. Where applicable, we will also conduct cross-tabulations and comparative analyses of variance based on selected key characteristics of the study participants (e.g., sex, age categories, baseline opioid requirement). This is a pilot study aimed at producing preliminary data which will inform future large-scale studies. Our analyses will be purely descriptive and we will not attempt to show an effect size, thus there is no power calculation for this sample size, it is based on feasibility.

Our a priori hypotheses of the potential effect of patient characteristics on outcomes will be tested in subsequent large scale studies. The outcomes obtained in the proposed pilot study will also be compared with benchmark data based on the results of our previous studies with similar patient populations and other available recent or contemporaneous research and clinical data. Adverse events recorded in the study will be reported using both quantitative tabulations and qualitative descriptions.

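### For participants without withdrawal signs through Day 3, sections 6.9.4 and 7.4.3.1 start the prescribed buprenorphine at different times, which affects one descriptive secondary outcome (minor)

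*Combined protocol and SAP*

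**What the plan says.** Section 6.9.4 has two start rules. A participant with objective signs of withdrawal at a Day 1, 2 or 3 visit is sent a prescription "for a daily dose of BUP 16mg (BUP or BUP/NX 8/2mg: two SL) to start immediately". A participant who shows no withdrawal at any of those visits gets a prescription after the Day 3 visit, "with instructions to self-administer upon emergence of symptoms of opioid withdrawal or craving".

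Section 7.4.3.1 covers the same two groups. Those with signs get the prescription at the first visit where signs appear. For those without signs by Day 3, "the prescription will be written at the conclusion of that visit". The next sentence then describes one prescription, "2 films/tabs taken SL daily for each day, starting immediately", without saying which group it is for.

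Section 10.1 lists "time to next BUP dose" among the secondary outcome measures. It gives no event definition and no censoring rule.

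After Day 3 the only scheduled research contact is the Day 30 call. Section 6.9.9 says of it: "Participants will follow-up by phone at one month and again be asked to report adherence". A participant whose withdrawal returns between visits is told that "they may present to the Emergency Department for treatment" and is asked to report the visit to the study team.

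**The concern.** The case for a 32 mg load is that it lasts longer than a standard dose and gives time to arrange follow-up. Section 2.1.2 cites suppression of withdrawal for more than 72 hours after 24 mg, and for more than 3-4 days after 32 mg. The investigators therefore have reason to expect some participants to reach Day 3 without signs. Time to next dose is most informative in that group, and that is the group for which the two sections disagree.

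Two things are at stake. One is practical: a symptom-free participant may be told to start 16 mg/day at once or to wait, depending on which section staff read. The other is statistical: under one reading the recorded time reflects the return of symptoms, and under the other it reflects the visit schedule. If staff differ, the summary mixes the two.

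**Working it through.** No arithmetic in the plan bears on this. The check is to set the two sections side by side and follow each one through to the outcome.

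**1. Is it the same prescription?** Section 6.9.4 gives 16 mg daily. Section 7.4.3.1 gives two 8/2 mg units daily: 2 × 8 mg = 16 mg. The prescription is the same and only the start differs.

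**2. Start rule by group**

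| Group | Section 6.9.4 | Section 7.4.3.1 as written |
|---|---|---|
| Objective signs at a Day 1-3 visit | Immediate | Immediate |
| No signs through Day 3 | When symptoms or craving emerge | Immediate, after the Day 3 visit |

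Only the second row conflicts.

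**3. Does another section settle it?** Sections 4.1, 6.9, 6.9.1, 6.9.6 and 6.9.10 say when the prescription is issued or how long it should last. None says when a symptom-free participant takes the first dose.

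**4. What happens to time to next dose in the second row?**
- Under 7.4.3.1, a compliant participant doses at about Day 3, nominally 3 × 24 = 72 hours after the load. This is approximate, because the protocol gives no clock times or windows for Days 1-3. The dose date is then about the same as that of a participant whose signs returned on Day 3.
- Under 6.9.4, the dose follows the return of symptoms or craving, with no upper limit set by the schedule.

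**5. Could the later date be measured?** The call is at Day 30 ± 3, so Day 27 to Day 33. Measured from the Day 3 visit, the gap is 27 − 3 = 24 days to 33 − 3 = 30 days. Following 6.9.4 alone would give a meaningful date, but one that rests on recall over several weeks.

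**6. How far does it reach?** The primary endpoint is decided at the index visit. Objective 4 and 5.1.2 item 3 concern Days 1-3, and the disputed rule acts only once the Day 3 visit is over. The documents give no rate of reaching Day 3 without signs, so the number affected may be anything from 0 to 35.

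**7. A related wording gap.** Section 5.1.2 item 3 counts participants who need a buprenorphine prescription on Days 1-3 and does not exclude the one that everyone else receives by default at the end of Day 3. Read literally, it would count every participant who completes Day 3.

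**The case against.** The strongest defence is that 6.9.4 is the dosing section and should govern. It separates the groups plainly, while 7.4.3.1 is a visit schedule whose phrase echoes the 6.9.4 wording for participants with signs. The sentence also ends in an unmatched bracket across a page break, so its structure may have been damaged. This is a fair guess at what was intended. But 7.4.3.1 is what staff would have open at the Day 3 visit, the sentence follows directly on the group without signs, and the protocol does not say which section prevails.

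The second defence is about size, and most of it stands. The outcome appears once, in a list in 10.1, and is not developed in 5.1.2. The analysis is descriptive and the sample size rests on feasibility. A descriptive summary still has to mean one thing, but the consequence is limited.

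A reader might infer that the trial could no longer tell lasting effect from a Day 3 return of withdrawal, or that the duration objective fails. The documents do not support either. COWS and craving are assessed at the Day 3 visit, and 5.1.2 item 3 tabulates signs, craving and time to occurrence separately. Only the date of the next dose fails to separate the groups.

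On the prescription count, one can answer that a required prescription naturally excludes a default one. That is probably what was meant, and it takes one clause to say so.

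**Conclusion.** Wrong as written, and minor. The two sections give incompatible start instructions for participants who reach the end of Day 3 without objective signs. If 7.4.3.1 is followed, their time to next dose is fixed at about Day 3 by instruction and says nothing about how long the load lasted.

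The effect is confined to one descriptive secondary outcome. Its size cannot be estimated, because the documents give neither the proportion reaching Day 3 without signs nor any indication of which section staff follow. The conclusion assumes that participants do as they are told and that 7.4.3.1 is read as it stands. If every site already applies 6.9.4, the outcome is not distorted by the start rule, but it still lacks a definition and depends on dates recalled at Day 30.

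**What to change.** 1. **Section 7.4.3.1.** Limit the immediate start to participants with objective signs. State that those without signs through Day 3 take the first dose when symptoms or craving emerge, as in 6.9.4.
2. **Section 10.1.** Define the event as the first buprenorphine dose actually taken after the load, wherever it was given, including at an unscheduled ED visit. Issue of a prescription is not part of the event. Censor participants with no reported dose at their last attended Day 1-3 visit, which is Day 3 for completers. Summarise by Kaplan-Meier so that loss before Day 3 is handled, noting the assumption that such loss is unrelated to dosing. List later dates recalled at Day 30 as supportive.
3. **Section 5.1.2 item 3.** Count only signs-triggered prescriptions as required, and tabulate the default end-of-Day-3 prescription separately.

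Optional tidying: 4.1 asks for reported symptoms as well as objective signs before early issue, while 6.9, 6.9.1, 6.9.4 and 7.4.3.1 ask for signs only. These could be aligned.

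The cost is wording in three places and one derived variable for prescription type, with no new visits. The downside is that the main summary does not describe time to next dose beyond Day 3. With the event limited to doses taken, a participant whose signs appear at the Day 3 visit is also censored there unless a dose has already been reported. That contrast has to be read from 5.1.2 item 3. Item 1 is still needed with item 2 in place, because it settles what participants are told and gives the supportive later dates their meaning.

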#### **7.4.4 Final Study Visit (Phone)**

##### ***Final Study Phone Check In (Day 30+-3, 30 minutes)***

- A healthcare utilization review and health questionnaire will be conducted to collect information on the type and amount of services received by participants.
- Functional outcome will be assessed using tools selected from the Study Measures.
- Attendance at follow-up treatment appointment within 1 month will be assessed by participant self-report and verified by contact with the provider.
- Participants will be assessed for adverse events, which will be recorded and reported.

At the conclusion of the study, the specifics of continued treatment will be a joint decision between the participant and the provider and will be managed by providers on a case-by-case basis. These decisions will not be reported to the study team. The novel part about this study is the induction strategy, but patients will otherwise be maintained on BUP in accordance with the standard of care. If patients wish to continue treatment, they will be connected with follow-up. The decision to continue will be a joint decision between the patient and provider.

##### ***Unscheduled Visit***

If a patient is experiencing objective signs of withdrawal outside the hours of one of their research visit appointments, they may present to the Emergency Department for treatment. They will be asked to report this visit to the study team. The PI may be contacted 24 hours a day, seven days a week.

#### **7.5 Concomitant Medications, Treatments, and Procedures**

Concomitant therapy/medications will be evaluated and reviewed on an individual basis by the PI. See inclusion/exclusion criteria in Section 6. All concomitant prescription medications taken during study participation will be recorded on the study record in REDCap. For this protocol, a prescription medication is defined as a medication that can be prescribed only by a properly authorized/licensed clinician. Medications to be reported in the CRF are concomitant prescription medications, over-the-counter medications and non-prescription medications.

##### **7.5.1 Precautionary Medications, Treatments, and Procedures**

Patients will be made aware of the risk of using other sedating substances such as alcohol or benzodiazepines while taking BUP, as these may increase the risk of over sedation and respiratory depression. They will also be made aware of the risks of using other opioids, as the concomitant use of BUP and full-agonist opioids will precipitate withdrawal.

##### **7.6 Prohibited Medications, Treatments, and Procedures**

Patients will be prohibited from participating in this study if they are already receiving treatment for OUD with methadone, naltrexone, or BUP, or are already prescribed other opioids for pain. They will be forbidden from initiating any of these medications during the study, except for the BUP prescribed by the researchers.

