#### **5. To explore treatment effect**

To provide preliminary treatment effect data, we will assess outcomes using measures employed in our other studies, such as linkage to treatment, quality of life, and additional patient-level outcomes (drug use, overdose events, healthcare use) at 30 days.

Preliminary data of treatment effect using outcomes measures employed in our other studies will be collected and assessed. We will explore the effect on initial linkage to and engagement in addiction treatment, quality of life and functional outcomes, and additional patient-level outcomes (drug use, overdose events, healthcare use), including but not limited to the following:

- a. the proportion and confidence intervals of participants of patients engaged in treatment at 30 days, with time to initial linkage to treatment assessed secondarily;
- b. changes in self-reported non-medical opioid use over first 30 days using the timeline follow back method;
- c. changes in patient reported outcomes (using scales such as PROMIS GLOBAL-10 and Treatment Effectiveness Assessment (TEA)), self-reported healthcare utilization (non-study health services form) and overdose events.

These measures will be participant self-report of engagement in treatment, confirmed by the treatment provider, or by direct contact with the facility and/or treating clinician and/or through EMR abstraction. Linkage to addiction treatment will be defined as receipt of an encounter for formal addiction treatment after the index ED visit. Engagement in addiction treatment will be defined as enrollment and receiving formal addiction treatment on the 30th day after the index ED visit. Formal addiction treatment will be those treatments consistent with the American Society of Addiction Medicine's (ASAM) level of care (1-4) and will include a range of clinical settings, including office-based providers of BUP or naltrexone, OTPs, intensive outpatient, inpatient, or residential treatments.

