## 6.2 Exclusion Criteria

An individual who meets any of the following criteria will be excluded from participation in this study:

1. Is currently engaged in medication treatment for OUD with methadone, BUP, or naltrexone
2. Currently requires prescribed opioids for treatment of an ongoing pain condition
3. Has a known allergy to BUP
4. Is pregnant as determined by hCG testing at the index ED visit
5. Is breastfeeding as determined by self-report
6. Has medical, psychiatric, or concurrent substance use conditions or severe cognitive impairment that might preclude safe participation in the study as determined by the study clinician or the clinical provider, or such that they are unable understand the study procedures and provide written informed consent to participate in the study
7. Is a prisoner or in police custody at the time of the index ED visit
8. Has previously enrolled in the current study

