#### **6.7 Participant Withdrawal or Termination**

##### **6.7.1 Reasons for Withdrawal or Termination**

Participants are free to withdraw from participation in the study at any time upon request. An investigator may terminate participation in the study if:

- After the first 8 mg dose of BUP is administered, a study participant experiences any clinical AE (e.g., allergic reaction) that would preclude safe administration of the subsequent BUP 24mg dose during the index visit. The initial BUP 8mg is a standard dose used in the ED; it is only the subsequent BUP 24mg (for a total dose of BUP 32mg) that is being evaluated in this study.
- Thus, if a participant develops a reaction to the initial 8mg dose, the reaction would be attributed to the standard dose of BUP and not the larger dose of being tested.
- The participant meets an exclusion criterion (either newly developed or not previously

Study Number: s19-01700

Version: 7.0

Version Date: 08/01/2022

recognized) that precludes further study participation.

- The participant becomes a prisoner.

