### **6.7.2 Handling of Participant Withdrawals or Termination**

If participants are terminated from the study or withdraw themselves for any of the above reasons, the situation will be handled accordingly. If participants choose to withdraw themselves, but have no AEs, they will still be eligible to continue treatment for OUD, which may include BUP, and will be treated with the standard of care and connected to follow-up as clinic availability allows. If participants are terminated or removed due to any AE, they will be monitored and treated either in the ED or on an outpatient basis. If a participant meets exclusion criteria (either newly developed or not previously recognized), they will be formally withdrawn from the study, but may be still be eligible to continue BUP treatment outside of the study. If participants are withdrawn or discontinued early, enrollment will continue to meet a goal of 35 participants.

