#### **8.4.4 Reporting of Pregnancy**

As detailed previously, pregnant women will not be included in this study. If any of the study participants become pregnant, however, it will immediately be reported to ND or IDE sponsor, study leadership, IRB, and regulatory agencies. Pregnant patients will be managed with the help of experts, and on an individualized basis. OUD treatment can be continued throughout pregnancy, but patients must be aware of the risks to the fetus, both of continuing treatment and abruptly discontinuing treatment. Participants who become pregnant during the study will be retained in the study, unless they voluntarily remove themselves.

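### Section 7.6 forbids starting methadone or naltrexone during the study, yet the Day 30 engagement endpoint counts naltrexone and OTP care as success, and no rule says how such participants are counted

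*Combined protocol and SAP*

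**What the plan says.** Section 7.6 bars people already treated with methadone, naltrexone or BUP, or prescribed other opioids for pain, and then adds: "They will be forbidden from initiating any of these medications during the study, except for the BUP prescribed by the researchers". It attaches no consequence to a breach. Section 6.5 sets individual participation at one month including follow-up.

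Section 5.1.2, item 5, makes the proportion engaged in treatment at 30 days secondary endpoint 5a. Engagement means being enrolled in, and receiving, formal addiction treatment on day 30. The qualifying treatments "will include a range of clinical settings, including office-based providers of BUP or naltrexone, OTPs, intensive outpatient, inpatient, or residential treatments".

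Exclusion 1 in section 6.2 reads: "Is currently engaged in medication treatment for OUD with methadone, BUP, or naltrexone". Exclusions 4 and 7 in the same list are tied to the index ED visit; exclusion 1 is not.

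Section 6.7.2 states: "If a participant meets exclusion criteria (either newly developed or not previously recognized), they will be formally withdrawn from the study". It also states: "If participants are withdrawn or discontinued early, enrollment will continue to meet a goal of 35 participants". Section 6.7.1 introduces its list of reasons, which includes a newly developed exclusion criterion that precludes further participation, with softer words: "An investigator may terminate participation in the study if".

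Section 6.9.4 refers every participant to a non-study provider of opioid use disorder (OUD) treatment and leaves continued BUP to that provider and the participant.

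**The concern.** The study is meant to move people into ongoing care, and endpoint 5a measures whether that happened. A participant who starts naltrexone with an office-based prescriber, or methadone at an OTP, meets the endpoint and breaks section 7.6 by the same act. If exclusion 1 is then read as newly met, 6.7.2 has that participant withdrawn and replaced.

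Neither section 5.1.2 nor the analysis plan in 10.1 defines the Day 30 denominator or says how someone who starts a prohibited treatment is scored. Different staff could follow different sections and obtain different proportions from the same data. Section 10.1 plans to compare outcomes with benchmark data and to use them in planning larger studies, so a proportion that depends on an unstated rule would be carried forward.

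**Working it through.** The plan gives no figure to reproduce. Section 10.1 sets the sample size of 35 by feasibility, and no engagement rate is stated. The check is first textual, then an illustration on assumed inputs.

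**Text side by side**

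1. Period: the ban runs during the study (7.6) and the study lasts one month for each participant (6.5). Day 30 falls inside it.
2. Overlap: naltrexone is forbidden in 7.6 and named in 5a. Methadone is forbidden in 7.6 and enters 5a through OTPs.
3. No overlap: residential, inpatient and intensive outpatient care count in 5a and are not forbidden as such. Opioids for pain are forbidden and do not count.
4. BUP: the ban is on initiating. BUP started by the study and continued by the referred provider (6.9.4) need not be a new initiation.
5. Consequence: 7.6 gives none. Withdrawal follows only if exclusion 1 is treated as newly developed under 6.7, where 6.7.2 makes it mandatory and 6.7.1 makes it discretionary.

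**Effect on the Day 30 proportion**

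Let e be the true engaged proportion and s the share of engaged participants who are on a prohibited medication. Both are assumed.

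- Kept and counted as engaged: e
- Withdrawn and removed from the denominator: e(1 − s) / (1 − e·s)
- Kept in the denominator but scored as not engaged: e(1 − s)

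With e = 0.50, removal gives:

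| s | Calculation | Reported |
|---|---|---|
| 0 | 0.500 / 1.000 | 50.0% |
| 0.25 | 0.375 / 0.875 | 42.9% |
| 0.50 | 0.250 / 0.750 | 33.3% |
| 0.75 | 0.125 / 0.625 | 20.0% |
| 1 | 0 / 0.500 | 0% |

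Over the same range of s, a true 30% reads between 30% and 0%, and a true 70% between 70% and 0%.

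**In counts, with exact (Clopper–Pearson) 95% intervals**

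Assume 18 of 35 are engaged, 9 of them through a prohibited medication.

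- Kept and counted: 18/35 = 51.4% (34.0 to 68.6)
- Withdrawn: (18 − 9)/(35 − 9) = 9/26 = 34.6% (17.2 to 55.7)
- Kept but scored as not engaged: 9/35 = 25.7% (12.5 to 43.3)

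With only 3 such participants, 51.4% becomes 15/32 = 46.9% or 15/35 = 42.9%.

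**Replacement**

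If withdrawn participants were replaced until 35 remained, enrolment would need to reach 35/(1 − e·s), rounded up. At e = 0.50 this is 40 for s = 0.25 and 47 for s = 0.50.

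**The case against.** The strongest reply is that exclusion 1 is an entry criterion. Applied literally after enrolment, it would also catch participants taking the BUP that the study itself prescribes, which cannot be intended. Section 6.7.2 opens by referring back to the reasons in 6.7.1, so its withdrawal rule may cover only exclusions that the investigator judges to preclude participation. This makes withdrawal an inference rather than a stated consequence. It does not remove the problem: 6.7.2 expressly reaches newly developed exclusions, and exclusion 1 carries no index-visit limit.

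Timing also limits the mechanism. No study visit is scheduled between Day 3 and Day 30, and attendance at treatment is assessed at the Day 30 call (7.4.4). Staff would often learn of outside treatment while recording the endpoint, too late for withdrawal and replacement beforehand. This makes replacement less likely, but it leaves open how the participant is counted.

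Finally, the stakes are modest: this is one descriptive secondary endpoint in a pilot without a power calculation. That stands, and it limits the weight of the point.

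A reader might infer three stronger claims that the documents do not support:

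- **Every participant who links to care breaks the protocol.** The planned hand-over of study-started BUP is not clearly forbidden, and several kinds of care that count in 5a are not banned.
- **The engagement result falls to zero.** That requires every engaged participant to be on a prohibited medication and to leave the denominator. No section says that withdrawn participants leave it.
- **The withdrawal rule also collides with section 8.4.4**, which says: "Participants who become pregnant during the study will be retained in the study". Exclusion 4 is tied to hCG testing at the index visit, so a later pregnancy does not meet it.

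**Conclusion.** The contradiction is real for naltrexone and for methadone through an OTP: section 7.6 forbids starting what endpoint 5a counts as success, and nothing in the documents resolves it. Sections 6.7.1 and 6.7.2 add a second inconsistency about whether withdrawal is optional or required. Together they allow successes to be removed and replaced.

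Wherever such a participant is removed, or scored as not engaged, the Day 30 proportion falls below what 5a defines. The size is unknown. In the assumed case of 9 among 18 engaged it is 51.4% against 34.6%, a difference of 16.8 percentage points; with no such participants it is zero. Both the number engaged and the share on a prohibited medication are assumptions.

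The primary endpoint is determined at the index visit (sections 3 and 3.1) and is not affected. The wording should be corrected, but the point does not threaten the study's main result.

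**What to change.** Reconcile sections 5.1.2 item 5, 6.2 (exclusion 1), 6.7.1, 6.7.2, 6.9.4 and 7.6. Which clinical rule on outside medication should stand is for the sponsor and investigator; this point takes no position on it. Whatever rule is kept, the text should:

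1. state which exclusion criteria apply only at entry and which can lead to later withdrawal, and use the same force in 6.7.1 and 6.7.2;
2. state in 5.1.2 and 10.1 that every dosed participant stays in the Day 30 engagement denominator and is scored by the 5a definition;
3. state that nobody is withdrawn from the analysis, or replaced, because they entered outside treatment;
4. say whether continuation of study-started BUP by the referred provider falls under 7.6.

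It would also help to tabulate engagement by type of treatment, so that readers can see how many successes came through a medication named in 7.6. The cost is protocol wording; no new data or participants are needed.
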